## 9.5.2. Thrombotic Microangiopathy

Cases of thrombotic microangiopathy, including thrombocytopenic purpura and hemolytic uremic syndrome, have been described with the proteasome inhibitors, bortezomib, carfilzomib, and ixazomib. The clinical presentation of thrombotic microangiopathy typically includes fever, microangiopathic hemolytic anemia (with schistocytes on blood smear), thrombocytopenia, renal failure, purpura, and neurological manifestations. Patients should be monitored for signs and

symptoms of thrombocytopenic purpura/hemolytic uremic syndrome. If the diagnosis is suspected, such as with any acute changes in renal function, thrombocytopenia or intravascular hemolytic anemia, interrupt zetomipzomib or placebo administration and evaluate (refer to Section 8.1.2). Missed doses should be addressed as per Section 6.1.3.2. If the diagnosis of thrombocytopenic purpura/hemolytic uremic syndrome is excluded, zetomipzomib or placebo may be resumed. If the diagnosis is confirmed, zetomipzomib or placebo must be permanently discontinued (refer to Section 8.1.2).

## 9.6. Unexpected Adverse Reactions

#### 9.6.1. Definition of an Unexpected Adverse Reaction

An unexpected adverse reaction is any untoward and unintended response that is related to the administration of zetomipzomib or placebo at any dose, which is not consistent with the applicable product information (eg, the Reference Safety information of the zetomipzomib Investigator's Brochure).

All suspected unexpected serious adverse reactions (SUSARs) will be subject to expedited reporting. The Sponsor or designee shall ensure that all relevant information about an SUSAR that is fatal or life-threatening is reported to the relevant competent authorities and IRB/IEC within 7 days after knowledge by the Sponsor of such a case and that relevant follow-up information is communicated within an additional 8 days. All other SUSARs will be reported to the relevant competent authorities and IRB/IEC within 15 days after knowledge by the Sponsor of such a case. All Investigators should follow SUSARs until the event is resolved or until, in the opinion of the Investigator, the event is stabilized or determined to be chronic. Post-study SUSARs that occur after the patient has completed the clinical study must be reported by the Investigator to the Sponsor.

## 9.7. Hypersensitivity Reactions

Hypersensitivity reactions are exaggerated or inappropriate immunologic responses occurring in response to an antigen or allergen. Drugs may cause allergic reactions by any mechanism of hypersensitivity. For example, penicillin may cause anaphylaxis, which is IgE-mediated, but most responses are trivial. Hypersensitivity reactions to zetomipzomib are not anticipated given its structure and mechanism of action; however, potential hypersensitivity to an excipient could occur. Studies in compound ONX 0914, an analog of zetomipzomib, demonstrated inhibition of T-helper 2 cell response and allergic reactions in foreign ovalbumin and house dust mite induced allergic airway inflammation in mouse models.

Known risk factors for developing a hypersensitivity reaction include allergic reaction history, concomitant diseases such as chronic respiratory diseases, cardiovascular diseases, mastocytosis or clonal mast cell disorders, and severe atopic disease. Some concurrent medications such as beta-adrenergic blockers and ACE inhibitors might also increase the risk. Patients in this study should be closely monitored. Should any signs and symptoms of suspected hypersensitivity reactions occur, the Investigator will diagnose per clinical guideline and zetomipzomib or placebo may be temporarily withheld. If the diagnosis of hypersensitivity is confirmed, zetomipzomib or placebo must be permanently discontinued, and the patient will be treated per clinical guidelines.

#### 9.8. Infections

The usual clinical care for patients with LN who use chronic immunosuppressives includes surveillance for severe or opportunistic infections, given the increased incidence in this setting. Patients with recent serious or ongoing infections are excluded from the study (Section 4.3). While zetomipzomib has not been associated with new onset or more severe infections to date in patients with similar risk factors, patients will be monitored for new infections, and potential infections (bacterial, viral, or fungal) will be fully evaluated. The periodic physical assessments in this study include capturing new onset signs and symptoms. Patients should be encouraged to contact the Investigator if they develop any new signs or symptoms between physical assessments. Clinical care will be provided for any newly diagnosed infection. Patients who use chronic prophylactic or suppressive therapy (eg, chronic antivirals for herpes simplex virus) as part of their usual care are permitted to continue with their usual therapies. Infections will be captured as AEs. In addition to inclusion in the safety database, the data on infections will be analyzed as part of the GTI (Section 7.2.2.8).

## 9.9. Independent Data Monitoring Committee

A study-specific IDMC will be used to enhance the safety and integrity of the study data for interim safety monitoring. The specific responsibilities and composition of the IDMC will be outlined in a separate IDMC Charter. The IDMC will be convened regularly, at least twice a year, and ad hoc.

It is the responsibility of the IDMC to weigh the risks and benefits throughout the study's duration. Specifically, this role includes the following: monitoring evidence for treatment harm (eg, toxicity, AEs, SAEs, and deaths) and requesting additional data analyses as necessary for the review process.

The IDMC will also examine efficacy and safety from the IA. Adjudication of CRR will be done by the Clinical Endpoint Committee (CEC) (see Section 9.10) and overseen by the IDMC, as described in the IDMC Charter. In addition, a Steering Committee will be formed to receive the IDMC recommendations.

## 9.10. Clinical Endpoint Committee

A CEC will adjudicate CRR (primary efficacy endpoint) by reviewing blinded data for patients in this study. The CEC will also assess treatment failure based on the criteria outlined in Section 2.2.5 The Sponsor will establish a CEC Charter describing the working procedures and responsibilities of the CEC. All adjudication decisions of the CEC will be appropriately documented.

#### 10. STATISTICAL ANALYSES

#### 10.1. Overview

Key elements of the statistical analyses for this study are described in this section; full details will be documented in a statistical analysis plan (SAP). The statistical analyses for this study will be the responsibility of the Biostatistics department of the Sponsor or its designee ( ).

The SAP will be written and approved prior to the first IDMC data review meeting and IA. The SAP may be revised or amended in accordance with subsequent protocol amendments or whenever deemed necessary. For the purpose of the primary endpoint and final data analyses, the primary endpoint and final database will not be unblinded until medical/scientific review has been conducted, protocol deviations have been identified, the data have been declared final and complete, and the SAP has been approved.

The following sections include a summary of the planned statistical analyses of the primary and secondary endpoints. Any substantive changes to the planned analysis procedures relative to those described in the protocol will be explained in the SAP and included in the clinical study report.

#### Baseline value:

Baseline UPCR will be determined by the average of the 24-hour collections at Screening.

Unless specified otherwise, baseline value for eGFR and other parameters including laboratory data is defined as the last value prior to the 1st dose of the zetomipzomib or placebo.

## **10.2.** Study Population Definitions

The following is a list of the main analysis populations.

**ITT Population**: The intent-to-treat (ITT) population consists of all patients who are randomized to the study. The ITT population will be the primary analysis population used for the efficacy analyses.

**Safety Population**: The safety population includes all randomized patients who receive at least 1 dose of zetomipzomib or placebo. The safety population will be the population used for the safety analyses.

**Per-Protocol Population**: The per-protocol (PP) population consists of all patients included in the ITT population who have no protocol deviations that may substantially affect the efficacy results. The final determination on protocol deviations, and thereby the composition of the PP population, will be made prior to the unblinding of the database and will be documented separately. The PP population will be used in efficacy analyses to support the primary efficacy analyses based on the ITT population.

# **10.3.** Sample Size and Power Considerations

A sample size of 249 patients with Class III/IV +/-V LN or 83 per treatment group (randomized in a 2:1:2:1 ratio for zetomipzomib 30 mg: placebo: zetomipzomib 60 mg: placebo) will have 80% power to detect a 20% difference (40% versus 20%) in CRR between zetomipzomib and placebo at Week 37 (9 months), using a 2-group binomial test (for pooled estimate of variance)

with a 0.05 2-sided  $\alpha$  level. The assumption of 20% for CRR in the placebo group was made based on the evaluation of relevant published data (Furie et al., 2020; Rovin et al., 2021).

The sample size calculation is intended for pairwise comparisons for zetomipzomib 60 mg versus the pooled placebo group and for zetomipzomib 30 mg versus the pooled placebo group, respectively. There is no statistical comparison between the 2 zetomipzomib dose groups. This sample size also reflects a planned IA for futility when approximately 50% of the randomized patients with Class III/IV +/-V LN have or would have completed the Week 37 visit (Section 10.3.1).

In addition to the 249 patients with Class III/IV +/-V LN, the study will also enroll up to 30 patients with pure Class V LN across the 3 treatment groups, for a total of up to 279 patients. The 30 patients with pure Class V LN were not included in the power calculation, as well as the assessments for type 1 error and multiplicity.

#### 10.3.1. Futility Boundary and Assessment

A futility assessment will be performed through an IA that is planned when approximately 50% of the randomized patients with Class III/IV +/-V LN have completed or would have completed the Week 37 visit with the primary endpoint assessment and prior to the completion of the target enrollment. The futility boundary using the Lan-DeMets (O'Brien and Fleming, 1979; DeMets and Gordon Lan, 2014) is non-binding and is shown in Table 5. The calculation was performed using . The futility boundary of  $\Delta$ =5.4% (4.7% conditional power at the observed value), will be assessed for the pairwise comparisons of zetomipzomib and placebo using an Intersection-Union approach. In this approach, futility will be declared if both  $\Delta 1 \le 5.4\%$  and  $\Delta 2 \le 5.4\%$  are true. Otherwise, futility will not be declared if either  $\Delta 1 > 5.4\%$  or  $\Delta 2 > 5.4\%$  is true. Here,  $\Delta 1$  and  $\Delta 2$  are pairwise differences in CRR at Week 37 between zetomipzomib 30 mg and pooled placebo and between zetomipzomib 60 mg and pooled placebo, respectively. A decision to stop the study for futility or to continue as planned will be reached after careful review of the data by the IDMC and the Sponsor's designated members (Steering Committee).

**Table 5:** Futility Boundary

Information Fraction	Cumulative β Spent at final analysis	Futility Boundary for Treatment Difference (Δ) in CRR at Week 37
50% randomized patients with Class III/IV +/-V LN	0.19786 (80.2% power)	5.4% (conditional power at the observed value according to =4.7%)

CRR=complete renal response; IA=interim analysis; LN=lupus nephritis; N=number of patients.

## 10.4. Background and Demographic Characteristics

Age, height, body weight, and other continuous variables will be summarized using descriptive statistics, while sex, race, age group, ethnicity, region, and other categorical variables will be provided using frequency tabulations. Medical history data will be summarized using frequency tabulations by Medical Dictionary for Regulatory Activities (MedDRA) system organ class and preferred term.

## **10.5.** Patient Disposition

Patient disposition (analysis population allocation, entered, completed, discontinued, along with primary reason for discontinuation) will be summarized using frequency and percentages. A summary of patients enrolled by site will be provided. Protocol deviations will be summarized using frequency tabulations.

## 10.6. Efficacy Analysis

The ITT will be the primary analysis population used for the efficacy analyses. Patients will be included in the treatment group to which they were randomized for the efficacy analysis using the ITT.

The primary analysis of each efficacy endpoint will be carried out for randomized patients (ITT) with Class III/IV+/- V LN (N=249). A supportive analysis using the PP population (Class III/IV+/- V LN) will be performed for key efficacy endpoints.

A sensitivity analysis for each of the selected efficacy endpoints (i.e., primary, key secondary and selected other efficacy endpoints) will be carried out for all randomized patients (ITT) including Class III/IV+/- V and pure Class V LN (N= up to 279) and nominal p-values will be presented for hypothesis tests.

Descriptive statistics for continuous variables will be summarized using the number of non-missing values (n), mean, standard deviation (SD), median, minimum, and maximum. Summaries will be presented for the change from Baseline, when appropriate. Categorical variables will be summarized using counts, percentages, and confidence intervals (CIs). All percentages will be based on the number of patients in the treatment group unless specified otherwise.

For time-to-event variables (eg, time to CRR, time to PRR, and time to UPCR ≤0.5), the Kaplan-Meier method will be used to estimate survival function, median survival time, and CIs. The log-rank test (stratified for the randomization stratification factors) will be used to compare between 2 survival curves. Cox's proportional hazards model will be performed to assess differences between treatment groups. The model will include terms for treatment and selected Baseline parameters including stratification factors. All statistical tests will be 2-sided, unless otherwise noted.

Binary efficacy endpoints (eg, CRR and PRR) will be analyzed using the Cochran-Mantel-Haenszel (CMH) test stratified by the randomization stratification factors (Section 3.2.1). Patients who have insufficient data for response determination for the time point under consideration will be handled using an estimand approach for intercurrent events or non-responder imputation (NRI), where appropriate for that time point.

Continuous efficacy endpoints (ie, change or percentage change from Baseline in UPCR by visit) will be analyzed using the longitudinal data analysis method based on a mixed model for repeated measures (MMRM) approach. This model will include fixed effect terms for randomized treatment, timepoint (ie, visit) and randomized treatment by timepoint interaction. Within subject error will be modelled by use of an unstructured variance-covariance matrix. Baseline value will be included as a covariate and the randomization stratification factors will be included as class terms. Treatment effect (ie, the difference in least-square mean values between

each zetomipzomib dose and placebo and the 2 zetomipzomib doses combined vs placebo) estimates will be extracted from the model by timepoint along with the associated 95% CIs and 2-sided p-values. A sensitivity analysis of this model by using multiple imputation (MI) for handling missing data will be performed. The influence of missing data over time will be assessed using multiple imputation techniques, specifically assuming missing at random and missing not at random (MNAR); for the latter both jump to placebo and tipping point MI analyses will be employed.

The Baseline value for 24-hour UPCR is defined as the average of non-missing 24-hour UPCR results from the Screening visit. Repeat test results will not be used to replace non-missing original test data. When only 1 non-missing sample 24-hour UPCR results from the Screening visit is available, then that single value will be used for the Baseline. Unless specified otherwise, baseline value for eGFR and other parameters including laboratory data is defined as the last value prior to the 1st dose of zetomipzomib or placebo.

In this study, all analyses involving treatment comparisons will be performed based on pairwise comparisons for zetomipzomib 60 mg versus the pooled placebo group and for zetomipzomib 30 mg versus the pooled placebo group. No statistical comparisons will be performed between the 2 zetomipzomib dose groups.

All analyses will be performed in SAS® v9.4 for Microsoft® Windows®.

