8.4.1. Analysis of Continuous Secondary Efficacy Endpoints

Continuous secondary efficacy endpoints include:

- Percentage change from Baseline in UPCR by visit
- Change from Baseline in clinical Systemic Lupus Erythematosus Disease Activity Index 2000 (SLEDAI-2K) score, excluding complement and anti-dsDNA components
- Change from Baseline in EuroQol 5-Dimension 5-Level (EQ-5D-5L) index score and EQ-VAS of general health.

Observed values of the continuous secondary efficacy endpoints will be analyzed using the longitudinal data analysis method based on a mixed model for repeated measures (MMRM) approach. The model will include fixed effect terms for randomized treatment, visit, and randomized treatment by timepoint interaction. Baseline value will be included as a covariate and the randomization stratification factors will be included as class terms. Within subject error will be modeled by use of an unstructured variance-covariance matrix. If the model does not converge using the unstructured matrix (TYPE=UN), the following variance-covariance structures will be tried in this order until convergence is achieved: Toeplitz (TYPE=TOEP), compound symmetric (TYPE=CS).

Treatment effect (ie, the difference in least-square mean values between each zetomipzomib dose vs pooled placebo and the 2 zetomipzomib doses combined vs pooled placebo) estimates will be extracted from the model by visit along with the associated 95% CIs and 2-sided p-values.

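### The MMRM uses one baseline slope for all visits while treatment contrasts are reported visit by visit; a baseline-by-visit term would protect precision, mainly for the change-from-baseline endpoints, at very small cost

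*Protocol*

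**What the plan says.** Protocol 10.6 lists the fixed effects: "This model will include fixed effect terms for randomized treatment, timepoint (ie, visit) and randomized treatment by timepoint interaction". It adds baseline as a covariate, the stratification factors as class terms, and the covariance: "Within subject error will be modelled by use of an unstructured variance-covariance matrix". In that section the only continuous endpoint named is change or percentage change in UPCR.

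SAP 8.4.1 repeats the structure: "The model will include fixed effect terms for randomized treatment, visit, and randomized treatment by timepoint interaction", and "Baseline value will be included as a covariate and the randomization stratification factors will be included as class terms". It applies the model to percentage change in UPCR and to two further secondary endpoints: "Change from Baseline in clinical Systemic Lupus Erythematosus Disease Activity Index 2000 (SLEDAI-2K) score, excluding complement and anti-dsDNA components" and "Change from Baseline in EuroQol 5-Dimension 5-Level (EQ-5D-5L) index score and EQ-VAS of general health". Treatment effect "estimates will be extracted from the model by visit along with the associated 95% CIs and 2-sided p-values".

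SAP 8.5.1 uses similar MMRM methods for the continuous exploratory endpoints. SAP 11 points to 8.4.1 for the UPCR summary at the interim analysis. Neither document lists a baseline-by-visit interaction.

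**The concern.** The model lets the treatment effect differ at each visit but holds the effect of baseline constant. Each visit's contrast is then adjusted with a slope averaged over all visits. A baseline measurement often predicts an early visit better than one a year later. Where that happens, the common slope over-adjusts at some visits and under-adjusts at others. The misfit adds to the variance of those contrasts and widens their intervals.

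What is at stake is precision for the continuous secondary and exploratory endpoints. With complete randomised data a common slope does not bias the contrast.

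**Working it through.** **Inputs from the documents.** Three groups of 83 with Class III/IV +/-V LN (Protocol 10.3), unstructured covariance, baseline as a main effect. SLEDAI-2K, EQ-5D-5L and 24-hour urine are scheduled after baseline at Weeks 13, 25, 37 and 53, and again at Week 56 (schedule of assessments). First-morning-void urine and laboratory tests are taken at 13 visits from Week 5 to Week 53. The documents give no SD, correlation or precision target for any MMRM endpoint.

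**The plan's own figure.** For CRR, 40% versus 20%, two-sided 0.05, 80% power: n = [1.960·√(2·0.3·0.7) + 0.842·√(0.4·0.6 + 0.2·0.8)]² / 0.2² = 81.2, so 82 per group. Power at 83 per group is 80.9%. The stated 83 and 80% are reproduced, but they have no bearing on the MMRM.

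**Formula.** Let b_t be the true baseline slope at visit t and R the covariance of the visits given baseline. Under unstructured covariance the common slope tends to

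β* = 1′R⁻¹b / 1′R⁻¹1.

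The adjusted difference at visit t uses β* where b_t is wanted, so

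variance ratio at t (common slope ÷ baseline-by-visit) = 1 + var(X)·(b_t − β*)² / R_tt.

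Analysing change from baseline shifts every slope by −1 and leaves the ratio unchanged.

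**Numbers (assumed).** Four visits, SD 1 throughout, correlations with baseline 0.7, 0.6, 0.5, 0.4. Then R_tt = 1 − b_t² = 0.51, 0.64, 0.75, 0.84. At the last visit:

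- residual correlation 0.3: β* = 0.589, ratio 1 + (0.4 − 0.589)²/0.84 = 1.042
- residual correlation 0.5: β* = 0.611, ratio 1 + (0.4 − 0.611)²/0.84 = 1.053
- residual correlation 0.7: β* = 0.661, ratio 1 + (0.4 − 0.661)²/0.84 = 1.081

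Square roots are 1.021, 1.026 and 1.040, that is 2-4% in interval width. At the third visit the variance ratios are 1.010, 1.017 and 1.035.

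**Range at the last visit.**

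| Assumed correlations with baseline | Variance ratio at residual correlation 0.3 / 0.5 / 0.7 |
|---|---|
| 0.50 at all visits | 1.000 / 1.000 / 1.000 |
| 0.60, 0.55, 0.50, 0.45 | 1.009 / 1.010 / 1.013 |
| 0.70, 0.60, 0.50, 0.40 | 1.042 / 1.053 / 1.081 |
| 0.80, 0.65, 0.50, 0.35 | 1.122 / 1.166 / 1.269 |

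Under AR(1) patterns with constant SD, the last-visit SE ratio is 1.041, 1.054 and 1.038 for lag-one correlations 0.9, 0.8 and 0.6. Simulation (83 per arm, 20% dropout completely at random, 600 trials, stratification factors omitted) gave 1.034, 1.057 and 1.042. A larger loss needs the SD to fall sharply as well: AR(1) 0.9 with SD falling to 60% of baseline gives 1.15 by formula and 1.24 by simulation.

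**Where the loss falls.** Not always late. Under AR(1) 0.5 the SE ratio is 1.030 at the first visit and 1.025 at the last.

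**Percentage change in UPCR.** In simulations with lognormal baseline UPCR of at least 1, with and without growing regression to the mean, the empirical SE ratio lay between 0.998 and 1.005 at every visit. A large-sample calculation applying correlations of 0.7 to 0.4 on the log scale gave 0.3-1.1% extra variance at the last visit. Only a much steeper decay (0.8 to 0.2) gave 3-9%.

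**Cost of the term.** Four visits add 3 parameters; 13 visits add 12. With truly equal slopes, the simulated SE changed by 0.5% or less.

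**The case against.** The strongest reply is that this is a refinement, since the documents contain no contradiction or error here. Much of that stands.

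- **Precision.** A reader might infer that the comparisons are less precise as planned. The documents cannot show that, because the loss depends on a baseline slope that changes over visits and they report nothing on it.
- **UPCR.** A reader might take UPCR, the lead continuous endpoint, as the main casualty. The endpoint listed is percentage change, for which the loss is likely near nil.
- **Late visits and the steroid taper.** A reader might expect the misfit at late visits because corticosteroids are tapered. The recommended maximum (Protocol Table 2) is already 10 mg/day at Week 13, the first post-baseline visit for SLEDAI-2K and EQ-5D-5L, and 5 mg/day at Week 17. The taper is therefore weak support for changing slopes at the modelled visits, and the loss can be largest at the first visit.
- **Main conclusions.** A reader might infer a threat to these. The primary and key secondary endpoints use CMH tests. Futility uses CRR differences, and sample-size re-estimation uses conditional power from the CMH statistic. The continuous endpoints carry nominal p-values only (SAP 8.1).
- **Cost.** The term is not literally free. It adds parameters to a model for which the SAP already plans covariance fallbacks (Toeplitz, then compound symmetry) if it does not converge.

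One defence fails. Both documents call the method longitudinal data analysis, which could mean that baseline is part of the response vector, so that the unstructured matrix would supply visit-specific slopes. Both also say that baseline is a covariate, so it does not.

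**Conclusion.** The point holds in conditional form and is minor. The specified model imposes one baseline slope on contrasts that are read visit by visit. If the true slope changes, the precision loss is about 4-8% in last-visit variance under correlations of 0.7 to 0.4 with equal SDs. It is about 1% under milder decay, 12-27% under the steep decay tabulated, and zero under a constant slope. All of these correlations and SDs are assumptions.

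The gain applies mainly to change-from-baseline endpoints: SLEDAI-2K, EQ-5D-5L and the exploratory laboratory measures. No confirmatory test or interim decision depends on it.

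**What to change.** Before unblinding, add a baseline-by-visit interaction to the MMRM in SAP 8.4.1, and to Protocol 10.6 if that is amended. State that it carries through to SAP 8.5.1; to cover the interim UPCR summary, the change must be made before that analysis. No new data or procedures are needed. The cost is the visits-minus-one parameters and the SE change of about 0.5% or less shown above. The existing covariance fallbacks can stay as they are.
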